3.2.1 Study materials and assessment process

A monthly pack will be provided that is matching the commercial configuration and presentation as approved by FDA, containing four weekly packs, full PI and a reserve Podhaler device in a case. Each weekly pack contains a Podhaler device, seven daily blister cards and the PIL which contains the IFU. Although only one dose is to be used by each subject, a monthly pack is provided in order to simulate the package that patients would receive when their prescription is filled; the HF assessment includes consideration of whether the subject can access and use the device and capsules when they are provided in a representative commercial configuration and presentation. Subjects will be given the opportunity to familiarize themselves with the study materials and labeling in advance of the first TOBI Podhaler use, and at any point during the dosing procedure, just as they would if using the product for the first time in reality. During the subject's (or subject and caregiver's) preparation and usage of placebo capsules and the Podhaler device, the HF Interviewer and HF Observer will independently complete a HF Assessment Checklist to capture data on use errors and close calls on all tasks as listed in [Appendix 5](#). Both the HF Interviewer and HF Observer will watch closely and intervene should

the subject or caregiver be acting in a way which may endanger the subject's health or well-being. Furthermore, a member of the investigational site staff qualified for performing clinical trials, including assessment for medical safety, will be present during the study assessments to support monitoring of the subject's health or well-being from a clinical perspective (could be the HF Observer).

Used capsules will be collected by the HF Interviewer, double checked for remaining amount of powder and placed in order of use into a custom photo fixture to create a digital photographic image. This visual assessment will be done before the post-dose discussion in order that any failure to empty the capsules can subsequently be addressed and root cause established. The images will be stored at the investigational site. Backup copies of the image files will be labelled with the subject identification number, taken and held at a specialist vendor performing the HF evaluation in order to allow further analysis if required; these images will be destroyed after a period of time as permitted by local and study guidelines.

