13.6.2 Critical use error - Clinically significant under-dosing

With regard to the hazard associated with under-dosing, only substantial variations in dose delivery to the lung present potential for harm to the user ([Molimard et al 2003](#), [Newman et al 2005](#)).

Following this approach, in the case of TOBI Podhaler:

- Sub-optimal techniques that will not significantly negatively impact on therapeutic outcome are not critical use errors. For example, failure to exhale fully prior to inhaling through the Podhaler device is not a critical use error.
- Occasional single instances of no powder being delivered to the lung from a capsule, as a result of a task performance error (e.g. physical slip or memory lapse) are not critical use errors. For example, a single instance of forgetting to pierce a capsule is not a critical use error.
 - This would be true for any capsule-based dry powder inhalation system, except for one that delivers an acute ‘rescue’ medication where failure to deliver a single dose could have immediate clinically significant consequences.
 - In the case of TOBI Podhaler, the impact of occasional instances of powder delivery errors is further reduced because each dose requires four capsules to be used. An error on a single capsule therefore affects only a quarter of a dose of powder.
- Difficulties or task failures that the user is aware of are not critical use errors. For example, difficulty removing TOBI Podhaler capsules from blister cards is not a critical use error. The user will be aware that they have not administered a dose and can seek assistance from their physician or nurse. They will address, rather than repeat, the task failure.

Critical use errors with the potential to result in clinically significant under-dosing all require routine repetition.

[Table 13-2](#) lists the critical use errors that could lead to the potential for clinically significant under-dosing that the user remains unaware of. For a comprehensive list with discussion of the criticality of all use steps refer to [Appendix 5](#).

Table 13-2 Critical use errors relating to clinically significant under-dosing

Aspect of Use	Description of critical use error	IFU Content
Capsule Piercing	Routine failure to adequately pierce capsules.	Step 9
	Routine failure to release blue button before inhalation.	Step 9
	Routine multiple piercing of capsules	Step 9

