13.10.1 Performance-based validation

The subject or subject/caregiver pair will be given a TOBI Podhaler monthly pack in a representative commercial configuration. They will be given the opportunity to familiarize themselves with the study materials and will then demonstrate taking a dose from the Podhaler device using placebo powder-filled capsules. No training will be given.

Subjects will then be asked to demonstrate administration of a dose. Subsequently, after all tasks are completed, the HF Interviewer will conduct a discussion to establish root cause of any misunderstanding (i.e. errors or close calls), in order to establish whether they can be attributed to the product interface.

The goal of the routine dose administration task is oral inhalation of the powder contents of four capsules using the Podhaler device. All capsules used by subjects will be inspected by the HF Interviewer after use in order to assess the degree to which the subject has successfully emptied them and achieved the task goal. In all instances of inadequately emptied capsules, or fewer than 4 capsules being used, the interviewer will investigate further through discussion with the subject in order to establish root cause. The post-use inspection of capsules will be conducted after the subject has stated that they believe they have completed the dose administration task, in order to ensure that the capsule-inspection process does not influence their completion of the task.

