- Here's the monthly pack which you would receive from your pharmacist. I'd like you to imagine that you are at home, preparing to use TOBI Podhaler for the first time. You are free to take as long as you like to look at the package contents and familiarize yourself with them before you take a dose just as you would if you were at home – please try to pretend we're not here. This isn't a test of whether you can guess how to use TOBI Podhaler or how quickly you do it. So please take whatever time you want to familiarize yourself with this monthly package and let me know when you're ready to prepare and take a dose. [Interviewer waits for subject (/caregiver) to indicate that they are ready.]
- Now I'd like you to prepare the inhaler and take a full dose from it just as if you had been prescribed with this medication. [To subjects and caregivers: "Please work together however you would in reality at home to prepare and administer a new medication." As appropriate, if the subject is 10 years or younger, the Interviewer will cite the labelling: "The instructions state that caregivers should help children who are 10 years of age and younger to use TOBI Podhaler, and should keep watching them use their TOBI Podhaler until they are able to use it the right way without help."] There's no hurry — you are free to take your time, pause and look at any of the package contents at any point, just as you would be at home.

Notes for Interviewer and Observer:

Interviewer and Observer will watch closely and intervene should the Subject or Caregiver be acting in a way which may endanger either of their health or well-being.

If the Subject or Caregiver put the capsule in the inhaler **without removing or replacing the mouthpiece** they may inhale the whole capsule and the Interviewer or Observer must intervene.

Other notes:

- If asked a use-related question the Interviewer will respond in a responsive but not leading manner, such as “what would you do if I weren’t here?”
- Interviewer and Observer will independently complete the assessment checklist.
- Interviewer will watch closely and note any areas of observed or reported difficulty so that they can be explored later.
- Each used capsule will be visually inspected by the HF Interviewer for the amount of remaining powder. This visual assessment will be done before post-use discussion in order that any failure to empty the capsules can be addressed and root cause established.

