- In addition, each capsule will be placed in a numbered container after use so that it can be kept for further analysis if required.
- It is possible that certain steps may not be carried out correctly because there is no drug being really taken – such as holding breath after inhalation (subjects may not ‘role play’ every step when they are not actually taking a dose of drug although requested to do so by the interviewer.) The interviewer should use his/her discretion to probe the reasons for subjects not following the steps correctly. If a user notes that they would have done a particular step differently if real medication were involved, this will be noted and analyzed and reported.

Post-use discussion

- How was your experience using TOBI Podhaler?
- Can you tell me more about that?
- Can you tell me about anything you found difficult? [If subject mentions confusion:] Why was it confusing?
- Can you tell me about anything you found easy?
[Interviewer will probe to discover root cause of all errors and, where possible, close calls. For example:
 - Do you think that you/your child received a full dose? Why/why not?
 - Can you tell me about checking the capsules?If the Subject or Caregiver mentions making a mistake, the Interviewer will probe:
 - Can you tell me why you did that?
 - Is there anything about the Podhaler device or instructions that encouraged you to do it?
- I’d like to ask you to look (again) at the instructions and tell me if there are any sections that are confusing or incomplete.
 - According to the instructions, how many capsules should you inhale each day?
 - What should you do if you think you or your child has not received the full TOBI Podhaler dose?

Before we finish, do you have any further questions or comments on the inhaler or the instructions? Then thank you again for your time.

17 **Appendix 5**

Task assessment and criticality table

Item	IFU step	Task	Assessment Method			Discussion of Task Step Criticality
			Inspection of Used Capsules	Observation of Task Performance	Questioning in post-dose discussion	

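### The full-dose question follows capsule inspection, so the evidence on whether users knew they had under-dosed is open to cueing

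*Protocol*

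**What the plan says.** **Criticality.** Protocol section 13.6.2 states: "Difficulties or task failures that the user is aware of are not critical use errors". It limits Table 13-2 to under-dosing that escapes the user's notice, and it also requires routine repetition. Section 13.11 applies the Appendix 5 criticality table in analysis. The SAP (section 1) leaves human factors analysis out of its scope, so the protocol is the only place where these rules appear.

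**Inspection.** Under section 3.2.1 the Interviewer collects the used capsules, which are "double checked for remaining amount of powder and placed in order of use into a custom photo fixture to create a digital photographic image". On timing, the same section says: "This visual assessment will be done before the post-dose discussion in order that any failure to empty the capsules can subsequently be addressed". Appendix 4 repeats the order: "This visual assessment will be done before post-use discussion in order that any failure to empty the capsules can be addressed".

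**Safeguard.** Section 13.10.1 says: "The post-use inspection of capsules will be conducted after the subject has stated that they believe they have completed the dose administration task". The reason given is "in order to ensure that the capsule-inspection process does not influence their completion of the task".

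**Belief question.** In the Appendix 4 post-use discussion, the instruction is "Interviewer will probe to discover root cause of all errors and, where possible, close calls. For example". The first example listed is "Do you think that you/your child received a full dose? Why/why not".

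**The concern.** If awareness helps decide whether an under-dosing failure counts as critical, the evidence on awareness should come from before anything that could tell the user how the dose went. Here the direct question comes afterwards. A user who left powder behind without knowing it, and who then sees the capsules held back, examined and photographed, may say that the dose was probably not complete. Read against section 13.6.2, that answer looks like a failure the user knew about, which argues for non-critical.

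The influence would run mainly one way, towards apparent awareness and so towards a more favourable view of the interface. It would also fall on a part of the instructions that this study is meant to validate. Section 13.5.2 reports that the capsule check was poorly understood in study CTBM100C2412 and that the instructions were changed to clarify it.

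**Working it through.** The plan states no figure for this point. It sets no hypothesis test and no pass rate (sections 9.4 and 9.4.2). The check is therefore a comparison of sections, followed by some arithmetic for context.

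**1. Order of events**

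| Step | Source | Scripted in Appendix 4? |
|---|---|---|
| Subject says they are ready to start | Appendix 4, HF assessment | Yes, the Interviewer waits for it |
| Subject performs the dose | Appendix 4, HF assessment | Yes |
| Subject states belief that the task is complete | 13.10.1 | No |
| Capsules collected, checked, photographed | 3.2.1; Appendix 4, Other notes | Inspection yes; photograph only in 3.2.1 |
| Question on having received a full dose | Appendix 4, Post-use discussion | Yes, as an example probe |

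The start of the task has a scripted prompt and the end has none. The only scripted belief question is in the last row.

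**2. Does awareness bear on classification?** Yes, through section 13.6.2. It is not the only criterion:
- Routine repetition is also required.
- For most piercing and inhalation steps, Appendix 5 makes a repeated, uncorrected error critical, which is a rule about behaviour.
- Section 3.2.2 gives, as an error unlikely to recur, a slip that the subject both notices and puts right. Doubt voiced after the session corrects nothing.

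The protocol does not say how the awareness rule and the behavioural rule combine, or what evidence establishes awareness.

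**3. Is belief captured before inspection?** In part. Section 13.10.1 requires a statement of completion and defines the goal of the task as inhaling the powder from four capsules. A user who declares the task complete while powder remains has given evidence of being unaware. However, the statement has no line in the interview guide and no item in the Appendix 5 table, and no section says that it decides awareness. Saying that one has finished also differs from believing that every capsule was emptied.

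**4. Could inspection cue the answer?** No section says that the result is shown or told to the user, and none says that inspection is done out of sight. Section 3.2 seats the subject in the interview room with the Interviewer and Observer. Cueing is possible but not established.

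**5. Would an error go unseen?** No. Section 13.10.1 requires every inadequately emptied capsule to be explored in discussion. Section 13.6.2 and Appendix 5 (item 17) require full reporting.

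**6. Context from study CTBM100C2412 (section 13.5.2).** Inputs: n = 45, of whom 31 emptied all four capsules; 8 failed through not understanding the capsule check. The exact 95% interval for x out of n runs from the 2.5% quantile of Beta(x, n − x + 1) to the 97.5% quantile of Beta(x + 1, n − x).
- Not all emptied: 45 − 31 = 14; 14/45 = 31.1% (18.2% to 46.6%).
- Check not understood: 8/45 = 17.8% (8.0% to 32.1%).

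If those rates recurred (an assumption), 8 to 14 of 45 subjects would have failures whose classification could turn on awareness. That is 15 × 8/45 = 2.7 to 15 × 14/45 = 4.7 per age group of 15. Neither count measured awareness, and the instructions have since been revised. These numbers show how many cases might be in play, not how many would be misclassified.

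**The case against.** The strongest reply is that belief is already obtained before inspection. Section 13.10.1 requires it, and the script asks the subject to take a full dose, so a declaration of completion carries that meaning. Sessions are recorded on audio and video, so the declaration can be recovered. No section makes the full-dose question the test of awareness. The example of a known failure in section 13.6.2 is trouble with the blister card, where the user plainly has not taken the dose; it is not doubt voiced later. All used capsules are inspected for every subject, so inspection alone does not signal failure, and users are themselves told to check capsules. The Interviewer must not prompt or lead. Everyone with an unemptied capsule, or fewer than four used, will be questioned, so the probe's example status matters less where it counts. Asking about a full dose while capsules are still in hand could itself prompt re-checking.

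Most of this stands and limits the point. It does not close the gap. The completion statement is unscripted, has no checklist item and is given no role in judging awareness, and its stated purpose is to protect completion of the task, not later answers. The instruction not to lead governs how questions are put; it cannot undo what the user has seen.

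A reader might go further and infer that the awareness evidence is contaminated, or that under-dosing failures would be lost. The documents support neither. Cueing is not shown to occur, and the failures remain recorded, investigated and reported whatever class they receive.

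**Conclusion.** The point holds as a cheap improvement. The only scripted belief question follows inspection, awareness bears on criticality under section 13.6.2, and the protection in section 13.10.1 is partial. The answer is therefore open to cueing towards apparent awareness. What is at risk is the criticality classification of an under-dosing failure, not its detection.

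The conclusion rests on two readings: that users may see the inspection, since no section prevents it, and that analysts may use the post-inspection answer when judging awareness, since no section excludes it.

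The size cannot be estimated from the documents. A reader might take the 8 of 45 from study CTBM100C2412, assume that inspection prompts 25% to 50% of such users to voice doubt, and conclude that 18% would fall to 13% (6/45) or 9% (4/45). That inference is not supported. The cue rate is invented, the 8 were counted for misunderstanding the check and not for being unaware, the instructions have changed, and the plan defines no such rate. Sample size and the descriptive analysis are unaffected.

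**What to change.** **Appendix 4.** Script the end of the task. When the subject or pair says that they have finished, record the task as ended. Then, before any capsule is collected, inspected or photographed, ask every subject or pair the neutral full-dose question. Enter both the completion statement and the answer on the Interviewer's and the Observer's checklists. Align the note on numbered capsule containers with this timing.

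**Sections 13.6.2 and 13.11.** State that awareness is judged from this pre-inspection statement and answer together with observed behaviour. State also that answers given after inspection inform root cause only and cannot by themselves move a failure to non-critical. The pre-inspection answer should not be the sole decider, because that would override what was observed.

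**Cost.** One script line moved, one checklist entry for the statement and answer, and two sentences of text. Some users may want to re-check a capsule or resume after the question; record this as prompted and do not count it as task performance.

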- instruction to inhale twice with each capsule. Most users will have sufficient inspiratory capability to empty a capsule with a single inhalation. The instruction to inhale twice mitigates the risk of incomplete powder clearance.
- instruction to inspect the capsule after use (step 17). This mitigates the risk of incomplete clearance of powder from a capsule that could be caused by omitted or inadequate piercing, inadequate inhalation or failure of device performance.

These are desirable actions, but not essential to dosing accuracy.

The instructions also contain general notes and warnings, and instructions on storage of the TOBI Podhaler. The revisions that were made to the IFU following the completion of CTBM100C2412 will be validated in this study. Revisions to the IFU general notes and warnings section which describe task steps will be assessed via observation of subjects' task performance, with any errors, difficulties or close calls addressed in post-use discussion to

establish root cause. Subjects will also be asked to review and comment on the clarity of the IFU, including revisions. Revisions which are not related to task steps will be assessed via comprehension questions.

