13.5.2 Summary of TOBI Podhaler IFU validation study CTBM100C2412

The IFU validation study was conducted in 2014-2015 in the US with 45 CF patients, accompanied by caregivers where the patient was aged 17 years or less. The study was conducted to meet the following PMR 1928-3: “An actual use human factors study to validate the approved IFU. The study will enroll 45 subjects in total with three age groups of approximately 15 subjects each: 6- 10 years, 11-17 years, and > 18 years. Only CF patients naïve to use of the Podhaler device will be enrolled. These subjects will not be trained prior to reading the IFU and will be observed during the study.”

The study showed that the majority of CF patients and/or their caregivers can understand and follow the approved IFU without prior training. All patients understood the basic sequence of operation of the Podhaler device: load, pierce and inhale.

Patients were asked to take one dose. Of the 45 patients, 31 patients emptied the powder from all 4 capsules completely. Of the 14 patients who did not completely empty the powder from all 4 capsules, 4 patients cleared more than $\frac{3}{4}$ of the total powder and 6/14 patients cleared approximately $\frac{3}{4}$; 4/14 patients cleared less than $\frac{3}{4}$ of the total powder.

Six of the 14 patients who did not empty the capsules failed for reasons which are not attributable to the IFU, such as failure to engage with the IFU or failure of the caregiver to understand that a child was not inhaling.

However, 8 of the 14 patients who did not empty the capsules failed because, following incorrect inhalation technique or piercing error, they did not understand the checking procedure outlined in IFU step 17 – in particular, what a correctly emptied capsule should look like.

Moreover, from observation some patients found this step difficult to navigate and understand and 10/45 patients mentioned confusion or difficulty around checking capsules in post-use discussion.

Misunderstanding the recommendation to inhale twice from each capsule was a contributory cause of failure in 4 cases, although it is evidently possible for some patients to empty the capsules with only one inhalation. 8/45 mentioned confusion or difficulty with the repeat inhalation step.

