Some IFU changes were recommended following the study, in particular to clarify the capsule check step and the requirement to inhale twice from each capsule. Changes were agreed with the FDA and are shown in the updated IFU in [Appendix 3](#).

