		Press blue button all the way down	Yes	Yes	Yes if correct performance is not observed	Potential for critical use error Use Error: failure to adequately pierce capsules. If this use error is repeated it has the potential to cause clinically significant under-dosing. Repeated uncorrected error is therefore critical. Occasional error is non-critical. (In this single-use assessment, all errors will be investigated, analyzed and reported.) (This use error can be rectified by users following step 17. Understanding of step 17 is recorded separately.)
		Release before inhaling	Yes	Yes	Yes if correct performance is not observed	Potential for critical use error Use Error: failure to release before inhaling. This use error results in no dose delivery from the affected capsule. Repeated uncorrected error is therefore critical. Occasional error is non-critical. (In this single-use assessment, all errors will be investigated, analyzed and reported.) (This use error can be rectified by users following step 17. Understanding of step 17 is recorded separately)
		Press only once	Yes	Yes	Yes if correct performance is not observed	Potential for critical use error Use Error: multiple piercing of capsule. If this use error is routinely repeated it has the potential to cause clinically significant under-dosing. The likelihood of significant under-dosing is very low, even if the use error is routinely repeated, but the potential does exist and therefore this use error is considered critical if repeated. (In this single-use assessment, all errors will be investigated, analyzed and reported.)
10	10	Breathe out completely	-	Yes (although note that it is not possible to ascertain through observation if a subject has	-	This task step is desirable, but not essential. Use Error: failure to exhale fully before inhalation. Avoidance of this use-error is desirable, but not essential. The instruction is a description of optimal technique. Sub-optimal technique in practice will not significantly negatively impact on therapeutic outcome.

Item	IFU step	Task	Assessment Method			Discussion of Task Step Criticality
			Inspection of Used Capsules	Observation of Task Performance	Questioning in post-dose discussion	
				exhaled completely)		

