		Appropriate response to any powder remaining in capsule: - re-inhale if more than coating remains, replacing capsule correct way	Yes	Yes	Yes if correct performance is not observed	
This task step is desirable, but not essential.
 
Use Error: failure to correctly re-insert capsule and repeat inhalation. Avoidance of this use-error is desirable, but not essential. The instruction is a description of optimal technique which reduces the risk of any capsules remaining inadequately emptied following earlier errors or failures in steps 5 to 15 above.
 
Note however that any failure to empty a capsule will be investigated in post-dose discussion, so that the root cause of failure can be determined, and fully reported.

		-re-insert and re-pierce if it does not appear to be pierced			Yes if correct performance is not observed	
This task step is desirable, but not essential.
 
Use Error: failure to correctly re-insert, re-pierce and re-inhale. Avoidance of this use-error is desirable, but not essential. The instruction is a description of optimal technique which reduces the risk of any capsules remaining inadequately emptied following earlier errors or failures in steps 5 to 15 above.
 
Note however that any failure to empty a capsule will be investigated in post-dose discussion, so that the root cause of failure can be determined, and fully reported.

		- use reserve Podhaler device if still does not appear to be pierced	-		Yes if correct performance is not observed	
Potential for critical use error.
 
Use Error: failure to use reserve Podhaler device in cases of capsules remaining inadequately pierced after correct re-insertion and re-piercing. This use error has the potential to cause clinically significant under-dosing and is therefore critical.

18	18	Repeat Steps 5 to 17 for 3 more times until your whole dose (4 capsules) has been taken	Yes	Yes	Yes if correct performance is not observed	
Potential for critical use error
 
Use Error: failure to administer four capsules per dose. If this use error is routinely repeated it will result in clinically significant under-dosing. Repeated error is critical. Occasional error is non-critical. In this single-use assessment, a failure to administer four capsules per dose will be viewed as

Item	IFU step	Task	Assessment Method			Discussion of Task Step Criticality
			Inspection of Used Capsules	Observation of Task Performance	Questioning in post-dose discussion	

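### The response to a non-empty or unpierced capsule in revised IFU step 17 can be seen only in subjects who meet one, and no scripted question covers the rest

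*Protocol*

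**What the plan says.** Section 13.5.2 of the protocol reports the earlier IFU study: "Of the 45 patients, 31 patients emptied the powder from all 4 capsules completely". Of the 14 who did not, 8 failed because, after an inhalation or piercing error, they did not understand the step 17 check, in particular "what a correctly emptied capsule should look like". The IFU was then changed, "in particular to clarify the capsule check step and the requirement to inhale twice from each capsule".

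Section 13.4.5 states: "The revisions that were made to the IFU following the completion of CTBM100C2412 will be validated in this study". It adds: "Subjects will also be asked to review and comment on the clarity of the IFU, including revisions".

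Appendix 5 item 17 covers the check itself and then "Appropriate response to any powder remaining in capsule", with rows for re-inhaling, re-piercing and using the reserve device. Questioning on these rows is called for when correct performance was not seen. Several earlier rows with potential for critical error (inadequate piercing, button not released, exhaling into the mouthpiece, poor lip seal, poor inhalation) say that step 17 can rectify the error and that "Understanding of step 17 is recorded separately".

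In the Appendix 4 post-use discussion, "Can you tell me about checking the capsules" is an example of a probe for the root cause of errors. Every subject is asked open questions about the experience, whether any instructions are confusing or incomplete, how many capsules to inhale per day, and what to do if the full dose may not have been received.

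Sections 6.5 and 9 of the protocol have each use step marked pass or fail and each checklist item summarised as a number and percentage of subjects. The SAP leaves all human factors analysis out of scope (SAP Section 1).

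**The concern.** The earlier failure was to accept a capsule that was not empty. When all four capsules empty, a user who understands step 17 and a user who would accept any capsule do the same thing: look, discard, go on. A pass on the check row does not tell them apart, and the response rows are never exercised.

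The script does not fill the gap. The question on an incomplete dose comes closest, but the IFU in Appendix 3 answers it with contacting the healthcare provider, not with re-inhaling or re-piercing. For subjects with only empty capsules, evidence on the response would depend on what the interviewer chose to probe.

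The denominator is also open. The protocol does not say how the response rows are marked when no response was needed. If such sessions count as passes, or stay in the denominator, the percentage mixes subjects who showed the response with subjects who never had to.

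**Working it through.** **Plan's own figures.** Three age groups of 15 give 3 × 15 = 45 completers (protocol Section 9.8). The earlier study's counts agree: 31 + 14 = 45, and 6 + 8 = 14. No hypothesis is tested, so there is no power figure to reproduce.

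**How many would show the response.** Section 13.5.2 gives 14/45 = 31.1% left with powder (exact 95% interval 18.2% to 46.6%). Applied here, that is about 14 of 45, or 14/3 = 4.7 per age group. Over the interval it is about 8 to 21 of 45. With Binomial(15, 0.311), a given age group has 3 or fewer such subjects with probability 27%.

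The 14 is illustrative only. It counts powder left at the end, so patients who met residue and corrected it are among the 31, in unknown number. The revised IFU could lower the number. I therefore also use 20 and 30 exposed.

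**Would a repeat of the old problem be seen?** Yes. Eight of 45 failed. At that rate, the chance of at least one such failure in 45 is 1 − (37/45)^45, over 99.9%, whatever the number exposed.

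**A smaller problem left after the revision.** Let p be the assumed share of users who would misjudge a non-empty or unpierced capsule. The chance that at least one is seen among n informative subjects is 1 − (1 − p)^n. With none seen, the one-sided 95% upper bound is 1 − 0.05^(1/n).

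| Informative subjects | p = 5% | p = 10% | p = 20% | Upper bound if none seen |
|---|---|---|---|---|
| 14 | 51% | 77% | 96% | 19% |
| 20 | 64% | 88% | 99% | 14% |
| 30 | 79% | 96% | over 99% | 10% |
| 45 | 90% | 99% | over 99% | 6% |

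The last row is a ceiling, because it assumes that the question exposes everyone who would misjudge. If it exposes only half, the question alone gives 1 − (1 − 0.025)^45 = 68% at p = 5%. Observation continues alongside it, however. With n exposed and the other 45 − n asked, the chance is 1 − 0.95^n × 0.975^(45 − n): 78% for n = 14, 81% for n = 20 and 85% for n = 30. The gain over observation alone is then 27, 17 and 7 percentage points.

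These figures count only a demonstration or a direct answer. They give no credit for observed checking or for comments on IFU clarity.

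**Denominator.** In the earlier study, 8 failures are 8/45 = 18% of all patients and 8/14 = 57% of those left with powder. The rate among all who met residue lies between these, and it cannot be computed because that count is not reported.

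**The case against.** Several points on the other side stand.

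- **The questioning rule may already cover it.** Read literally, it includes a subject who never had to re-inhale. Items 20 and 21 use the same rule with no observation marked for replacing or wiping the mouthpiece, so it is not confined to errors that were watched. Item 30 points the other way: observation applies only where a reserve device is needed, and comprehension is not re-assessed. The rule is ambiguous, not absent.
- **The checklist is not in the documents.** Section 6.5 says that it captures answers to comprehension questions. It could hold a question that the script lacks, and the script leaves the later discussion to the interviewer's judgment.
- **Criticality is limited.** Appendix 5 rates the check, re-inhale and re-pierce rows as desirable, and only the reserve-device row as potentially critical. Item 30 reports that all subjects in the earlier study understood reserve-device use.
- **The outcome that matters is measured in every session.** Used capsules are inspected and photographed (Sections 3.2.1 and 13.10.1), and every failure to empty is investigated and reported.

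A reader might infer that the revised step 17 goes unassessed, or that the study could miss the old problem. The documents and the calculation above support neither. A reader might also see a contradiction with item 25, where comprehension is asked again because the IFU wording changed. Item 25 cannot be observed in one session, whereas step 17 sometimes can, so this is a useful comparison but not an inconsistency. Nor does anything say that the report will claim a demonstration in all 45.

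What remains is that a session in which every capsule empties shows nothing about the response, and that no scripted question carries out the rule for those subjects.

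**Conclusion.** The point holds as a modest gap in the evidence, worth considering. The plan commits to validating the revised step 17. Direct evidence on the response will come only from subjects who meet a non-empty or unpierced capsule: about 14 of 45 if the earlier proportion applied, possibly more or fewer. The design would catch an unchanged problem.

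The gain is for a smaller residual misunderstanding. At an assumed 5%, observation alone gives a 51% to 79% chance of seeing a case for 14 to 30 exposed. Asking everyone gives at most 90%, or about 68% from the question alone if it exposes half. The result rests on the assumed share, on independent subjects, and on the exposed number, which the documents do not give.

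**What to change.** 1. **Appendix 4.** Just before the closing question, ask every subject or subject/caregiver pair one non-leading question: how would you tell whether a capsule is finished, and what would you do if it still held powder or was not pierced? A single photograph or spare placebo capsule may be shown. It should not be another patient's used capsule, given the cross-contamination risk in Section 3.7.2. Do not show a contrasting set of three, because the IFU pictures these states and the task becomes matching.
2. **Appendix 5 item 17.** State that this questioning applies when the response was never required, and record the answer apart from observed errors.
3. **Protocol Section 9 and the human factors report.** Give the observed item 17 response with the number of subjects who met a non-empty or unpierced capsule as denominator, overall and by age group. Mark the others as not required, neither pass nor fail.

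The cost is a few minutes in a session of about 60, one checklist entry and one reporting sentence. No new patients, visits or supplies are needed: a pack holds 4 × 7 × 8 = 224 placebo capsules and a dose uses 4. The downside is that a verbal answer is weaker evidence than observed use, and the question must come last so that it does not coach.
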